#### 4.2 Duration of Study

Study participants will have four scheduled study visits: Screening/Enrollment, Week 4, Week 24, and Week 28. At Screening/Enrollment, women will complete an interviewer-administered baseline questionnaire, urine pregnancy testing, HIV rapid finger stick testing, and blood for CD4+ T cell count and HIV-1 RNA testing for HIV positive participants, and will self-collect a vaginal brush for hr-HPV testing. Urine collected for pregnancy testing will also be sent for hr-HPV and S5 methylation testing (for research purposes only). HPV-positive women and every 10th consecutive HPV-negative woman will complete same-day VIA with colposcopically-directed cervical biopsy and endocervical curettage (ECC) (if lesion seen), and thermocoagulation if ablation-eligible by colposcopy. If no lesion is seen on colposcopy, the woman will have a cervical pap smear and ECC collected, and no thermocoagulation will be performed. Finally, women who are suspicious for cancer at VIA will undergo colposcopically-directed cervical

biopsies. All women who undergo speculum exam will undergo provider-collected cervical swab, which will be sent for hr-HPV and S5 methylation testing (for research purposes only).

All women who had cervical biopsy or cervical pap smear and ECC done at Screening/Enrollment will return at Week 4 for histology and/or cytology results. All women who had CIN1, CIN2, or CIN3 and underwent thermocoagulation will be asked to return for a follow-up visit at Week 24 post-treatment to assess for resolution of their HPV and cervical dysplasia. At Week 28 visit, women will receive their histology and/or cytology results and be referred as necessary.

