#### **Week 4**

All women who had cervical biopsies or cervical pap smear, and ECC done at Screening/Enrollment will return for histology and/or cytology results at Week 4. HPV-positive/VIA-negative women without CIN or ICC on histology and those with normal cytology will be advised to continue with routine ICC screening per guidelines. Women who underwent thermocoagulation will be evaluated for interval medical history or post-treatment adverse events during this visit. HPV-positive/VIA-negative women with CIN2+ on ECC or abnormal cytology on cervical pap smear will be referred to KCH Colposcopy Clinic for further management.

HPV-positive/VIA-positive women who had CIN detected at baseline cervical biopsy, and underwent thermocoagulation will be followed up at Week 24 post-treatment. Women who had CIN and visible cervical lesion that was not ablation-eligible by colposcopy or had ICC will be referred to KCH Colposcopy clinic for further management.

Women who are HPV-positive may be enrolled in and consented for IDIs at their Week 4 visit. These interviews will be conducted similarly to those done at the Screening/Enrollment visit but they will also cover women's experiences sharing their screening results with others and abstaining from sex for the recommended interval after biopsy/thermocoagulation.

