#### **Week 24**

All women treated by thermocoagulation and had CIN1+ detected by baseline cervical biopsy will return at Week 24 for colposcopy to assess for resolution of cervical dysplasia after thermocoagulation. HPV testing on a provider-collected vaginal brush will also be performed at Week 24 to assess for HPV resolution after thermocoagulation. If the colposcopy shows no visible lesions at this Week 24 visit,

cervical pap smear and ECC will be collected. If a lesion is observed during colposcopy, at least 2 but not more than 4 directed biopsies and ECC will be performed. Images may be captured via the EVA System. These images will be stored only in password-protected and de-identified study databases, linked only to the study participant PID. The images will be used for internal quality assurance and possibly shared in de-identified form for future research. All women who still have CIN2/3 or have developed CIS or ICC at Week 24 will be referred to KCH for additional management. Women will also be evaluated for changes in their interval medical history and post-treatment adverse events during this visit. Finally, all women who were referred to KCH Colposcopy Clinic will be followed up at this visit to ensure that they received the care they required.

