Undertreatment will be calculated as the proportion of women with CIN2+ at Screening/Enrollment who were not treated or referred via our screening algorithm due to a negative HPV and/or VIA result. This proportion will represent the women with CIN-2+ who were missed by our HPV-and-VIA-based algorithm. For undertreatment, we will also evaluate the proportion of women who underwent thermocoagulation but were ECC positive for endocervical CIN2+, and therefore needed to be referred for further management since thermocoagulation does not adequately treat endocervical dysplasia. We have based our hypotheses on a recent review, which found that the pooled estimates for VIA sensitivity and specificity were 0.69 (95% CI 0.54-0.81) and 0.87 (95% CI 0.79-0.92), respectively, as well as from the high false positive rate for VIA found in our pilot study with nurses and clinicians in Malawi. These performance measures, however, were for primary screening, rather than as referral to treatment among HPV positive women.

In addition, to assess the potential for undertreatment of HPV-positive women, we will conduct VIA at Screening/Enrollment for every 10th women who is hr-HPV

negative. This sub-set analysis of HPV negative women undergoing VIA will allow us to control for potential verification bias. As all women will not be referred for verification by colposcopy, using only the histology results on HPV positive women to estimate disease burden could lead to biased inference. To correct for this verification bias, we will utilize the colposcopy results among the random sub-set of HPV-negative women to employ the maximum likelihood method proposed by Zhou. Estimates using this method are valid provided that the histology data are missing at random. This assumption means that for women with the same test results, those who were referred to colposcopy were similar to those that were not. Corrected CIN2+ burden will be estimated using maximum likelihood estimators (MLEs). This secondary objective is largely descriptive and, thus, formal power calculations are not made.

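### At Week 4, high-grade disease on the baseline endocervical curettage triggers referral only for HPV-positive/VIA-negative women; ablated VIA-positive women have no explicit trigger, though the analysis plan says they need referral.

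*Combined protocol and SAP*

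**What the plan says.** Every woman with a lesion at colposcopy has biopsies and an ECC before any ablation, and women with no lesion have a Pap smear and an ECC (section 4.3, Screening & Enrollment). An ECC result therefore exists for all examined women at Week 4.

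Section 4.3 (Week 4) then gives three dispositions for women with abnormal results:

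- Referral on ECC or cytology: "HPV-positive/VIA-negative women with CIN2+ on ECC or abnormal cytology on cervical pap smear will be referred to KCH Colposcopy Clinic for further management".
- Referral on lesion type or cancer: "Women who had CIN and visible cervical lesion that was not ablation-eligible by colposcopy or had ICC will be referred to KCH Colposcopy clinic".
- Follow-up without referral: "HPV-positive/VIA-positive women who had CIN detected at baseline cervical biopsy, and underwent thermocoagulation will be followed up at Week 24 post-treatment".

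Section 6.3 (secondary objective I) counts ablated women with endocervical CIN2+ on ECC as undertreated. It says they "therefore needed to be referred for further management since thermocoagulation does not adequately treat endocervical dysplasia".

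At Week 24, section 4.3 refers regardless of VIA status: "All women who still have CIN2/3 or have developed CIS or ICC at Week 24 will be referred to KCH for additional management". It also checks on earlier referrals: "all women who were referred to KCH Colposcopy Clinic will be followed up at this visit to ensure that they received the care they required".

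Attendance at Week 24 is described in several ways. Section 4.3 (Week 24) ties it to the biopsy: "All women treated by thermocoagulation and had CIN1+ detected by baseline cervical biopsy will return at Week 24". Section 4.2 names no specimen: "All women who had CIN1, CIN2, or CIN3 and underwent thermocoagulation will be asked to return for a follow-up visit at Week 24 post-treatment". The schedule in section 5.1 likewise asks for CIN1 or worse at enrolment without naming a specimen.

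**The concern.** The written ECC trigger depends on VIA status, and no reason is given. VIA does not decide who is ablated: section 4.3 also ablates VIA-negative women whose colposcopic lesion is suitable. Two HPV-positive women, both ablated and both with CIN2+ on ECC, therefore get different Week 4 instructions solely because one was VIA-positive. By the plan's own account, ablation was inadequate treatment for both.

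What is at stake is mainly patient care: known high-grade endocervical disease could wait for months. Section 7.3 requires the protocol to be followed except in an emergency, so this referral should not rest on staff going beyond a rule that names another group.

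There is a smaller statistical consequence. Women referred and retreated before Week 24 affect the objective II cure rate, and section 6.3 does not say how they count. That question already arises for ablated HPV-positive/VIA-negative women, whom the present rule does refer.

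**Working it through.** **Tracing the referral rules.** Take non-invasive CIN2+ (CIN2, CIN3 or carcinoma in situ) on baseline ECC; invasive cancer has its own Week 4 trigger.

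| Woman | ECC/cytology rule | Lesion/cancer rule | Next step under section 4.3 |
|---|---|---|---|
| HPV-positive, VIA-negative, ablated | Met | Not met | Referred at Week 4 |
| HPV-positive, VIA-positive, ablated, CIN on biopsy | Not met (VIA-positive) | Not met (lesion suitable for ablation, no cancer) | Week 24 |
| HPV-positive, VIA-positive, ablated, CIN on ECC only | Not met | Not met | None stated under Week 24 |
| HPV-negative, sampled | Not met (HPV-negative) | Met only if CIN with a visible lesion unsuitable for ablation | Otherwise no referral stated; Week 24 if ablated with CIN on biopsy |

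For the second woman the gap to the next scheduled visit is 24 − 4 = 20 weeks. Referral then depends on disease found at Week 24, and those results are given at Week 28. The fourth woman has the same gap for cytology: if no lesion is seen she has a Pap smear, but the abnormal-cytology trigger does not name her.

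**Week 24 attendance, side by side.**

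- Section 4.3 (Week 4 and Week 24): ablated, with CIN on baseline biopsy.
- Sections 4.2 and 5.1: ablated, with CIN, no specimen named.
- Section 6.3, primary objective II, opening: all women who undergo thermocoagulation.
- Section 6.3, primary objective II, HPV paragraph: expects Week 24 HPV results for baseline CIN1 and for normal or cervicitis.

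These cannot all be the criterion. Under the first, the third woman has no efficacy visit; the others would bring her back.

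**Retreatment and the cure rate.** Inputs from section 6.2: 76 women with CIN2/3, 5% loss, 90% efficacy.

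- Evaluable: 76 × 0.95 = 72.2, which reproduces the plan's 72.
- Cured: 0.90 × 72 = 64.8, taken as 65. Baseline estimate 65/72 = 90.3%; not cured, 7.

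Let r women be retreated at the referral clinic before Week 24. The documents give no value, so r = 1, 3, 5 is assumed. The result depends on the counting rule and on what those women's outcome would have been without retreatment.

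| r | Count as not cured; otherwise cured: (65 − r)/72 | Count as not cured; otherwise not cured: 65/72 | Excluded; otherwise cured: (65 − r)/(72 − r) | Excluded; otherwise not cured: 65/(72 − r) |
|---|---|---|---|---|
| 1 | 64/72 = 88.9% | 90.3% | 64/71 = 90.1% | 65/71 = 91.5% |
| 3 | 62/72 = 86.1% | 90.3% | 62/69 = 89.9% | 65/69 = 94.2% |
| 5 | 60/72 = 83.3% | 90.3% | 60/67 = 89.6% | 65/67 = 97.0% |

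The range is 83.3% to 90.3% if they count as not cured, and 89.6% to 97.0% if excluded. One woman moves the estimate by 1/72 = 1.4 points when her status changes from cured to not cured.

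**The case against.** The strongest reply is that referral is plainly intended. Section 6.3 says so for exactly these women. The section 5.1 schedule has a row for giving results and referrals at Week 4, open to everyone who had a biopsy or smear with ECC. The enrolment text in section 4.3 refers women with suspected endocervical dysplasia, with no VIA restriction. A competent clinician would refer.

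The point about intent stands: a reader might infer that the protocol bars these women from referral, and it does not. But none of the three texts supplies the missing instruction. The section 6.3 sentence defines an analysis measure. The schedule row gives an occasion without a criterion. The enrolment sentence follows the colposcopic ablation criteria and concerns suspicion, before any histology exists.

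A second reply is that a woman with CIN on ECC only is not really lost, because sections 4.2, 5.1 and 6.3 all point to a Week 24 visit. That also stands. A reader of the Week 24 text alone might infer that she leaves the study; taken together, the documents show an inconsistency and not a settled exclusion.

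A third reply concerns the cure rate. If ablation does not treat endocervical disease, many of these women would be not cured anyway, particularly since ECC is repeated at Week 24 whether or not a lesion is seen. Counting them as not cured would then change nothing, and excluding them would raise the estimate. This is correct, so a claim that the gap biases the cure rate in a known direction is not supported. The objective II hypothesis speaks of the 24-week biopsy, which leaves open whether ECC counts.

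**Conclusion.** The gap holds as a narrow one: section 4.3 has no explicit Week 4 trigger on an ECC result for ablated HPV-positive/VIA-positive women, or for most sampled HPV-negative women, although section 6.3 says ablated women with endocervical CIN2+ need referral. It looks like a drafting omission and is worth correcting for safety.

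The number affected cannot be derived and is probably small. No rate of CIN2+ on ECC is given, and the ablation criteria (ectocervical lesion, visible squamocolumnar junction) select against endocervical disease. The sample size does not change, and the undertreatment proportion can be calculated either way.

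The inconsistent Week 24 criterion and the missing retreatment rule are secondary. The cure-rate figures are illustrative: r is assumed, and the 72 rests on minimum expected counts and includes women who may not have been ablated. They show that a counting rule is needed, and nothing about the direction of any bias.

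**What to change.** 1. Section 4.3, Week 4: refer to the KCH clinic any woman with CIN2+ on baseline ECC, whatever her HPV, VIA or ablation status. Extend the abnormal-cytology trigger to sampled HPV-negative women who have a Pap smear.
2. Sections 4.2, 4.3, 5.1 and 6.3: use one Week 24 attendance criterion for ablated women, at least covering CIN on baseline biopsy or ECC. If Week 24 HPV results are wanted from ablated women with normal or cervicitis histology, the criterion must include them too.
3. Section 6.3, primary objective II: state how a woman retreated before Week 24 counts. One workable rule is not cured by thermocoagulation, with a sensitivity analysis excluding her. State also whether Week 24 ECC counts towards cure.

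The cost is a wording amendment and a few sentences of analysis plan. The ECC result, the Week 4 visit and the referral route already exist. The downside is a few more referrals and Week 24 visits; if item 2 is extended to women without CIN, there would be more visits.

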#### **Week 24**

All women treated by thermocoagulation and had CIN1+ detected by baseline cervical biopsy will return at Week 24 for colposcopy to assess for resolution of cervical dysplasia after thermocoagulation. HPV testing on a provider-collected vaginal brush will also be performed at Week 24 to assess for HPV resolution after thermocoagulation. If the colposcopy shows no visible lesions at this Week 24 visit,

cervical pap smear and ECC will be collected. If a lesion is observed during colposcopy, at least 2 but not more than 4 directed biopsies and ECC will be performed. Images may be captured via the EVA System. These images will be stored only in password-protected and de-identified study databases, linked only to the study participant PID. The images will be used for internal quality assurance and possibly shared in de-identified form for future research. All women who still have CIN2/3 or have developed CIS or ICC at Week 24 will be referred to KCH for additional management. Women will also be evaluated for changes in their interval medical history and post-treatment adverse events during this visit. Finally, all women who were referred to KCH Colposcopy Clinic will be followed up at this visit to ensure that they received the care they required.

### **Week 28**

All women who had cervical biopsy or cervical pap smear, and ECC done at Week 24 will be asked to return at this visit for histology and/or cytology results and any necessary follow-up referrals to KCH Colposcopy Clinic.

### **Quality Assurance**

[name] [name], a pathologist at UNC-Chapel Hill, will re-review all biopsy specimens obtained during the study as a quality assurance measure. She will hold calls as needed with pathology staff at UNC Project-Malawi to discuss discrepancies between their specimen reviews.

### **Sample storage**

Participants' study-associated samples will be stored in the research laboratory at UNC Project-Malawi for future research on HPV infection and other biomarkers of cervical cancer to improve way to screen women for cervical cancer for a maximum period of 15 years. Samples will be stored de-identified using only study identification number with no personal information.

### **4.4 Expected Risks**

The following are possible risks due to participant enrollment into our study:

**4.4.1 Sample collection:** Risks to study participant include the physical risks from blood draw, vaginal and cervical sample collection, cervical biopsies, and ECC. Participants can experience pain, bleeding, and sometimes infection, and damage to tissue at the site of the sample collection. However, all these sample collections are done as part of routine clinical evaluations when indicated in women of reproductive age and are considered to be minimal risks.

**4.4.2 Treatment with thermocoagulation:** Risks include pain, infection, and damage to tissue at the site of treatment application, i.e., the cervix. These risks are considered minimal. Thermocoagulation is not associated with future fertility compromise or adverse pregnancy outcomes in future pregnancies.

Thermocoagulation is used for treating VIA-positive women in some cervical cancer screening programs including Malawi.

4.4.3 Psychological risks might arise if a participant's peer or partner finds out about her study participation and does not approve of it. In addition, participants might also have some embarrassment or discomfort providing urine samples; or answering sensitive questions during the survey, but they can opt not to answer such questions. Women who participate in the IDIs may have further risk of embarrassment or discomfort about answering sensitive questions, but they can opt not to answer and they will be assured that doing so will not affect their ability to remain in the study or receive necessary health care.

To address these risks, informed consent forms will be administered in Chichewa, the local national language that participants and study staff are fluent in, and only participants who demonstrate comprehension through a standard comprehension checklist will be enrolled in the study after providing written informed consent. During the informed consent process, participants will be counseled about the potential risks, benefits and side effects of study procedures. Only study staff trained in the Biomedical Research and Good Clinical Practices will be involved in the study. Study procedures, risks, and benefits will be discussed with study participants, and study staff will answer all questions prior to obtaining consent. Each woman will be fully informed regarding the reasonably foreseeable impact of the research on her circumstances.

Physical risks will be minimized by having qualified and experienced staff conducting study procedures. Sterile techniques will be applied to minimize risks of infection. The Study Coordinator/Physician and the PI, will also be available to manage any complications that may arise from study procedures. Psychological risks will be minimized by encouraging potential participants to disclose their study participation to their partners and by minimizing physical tracing of participants unless it is unavoidable, in which case we will only be using information that we received permission from the participants to use, particularly when there are safety concerns. Prior to the interviewer-administered questionnaire, participants will be instructed that they can choose not to answer any questions they are not comfortable with. We will also provide appropriate counseling for HIV, sexually transmitted infections, and urine pregnancy testing to minimize any risks associated with these. Referral for further services will also be used where necessary.

In addition, the confidentiality of all study records will be safeguarded to the extent legally possible. All laboratory specimens, reports, study data, and data collection forms will be identified by a participant ID number only to maintain participant confidentiality. All databases will be secured with password-protected access systems, and computer entries will be identified by participant ID only. Consents, the participant ID log link, and any other data forms that link participant ID

numbers to other identifying information will be stored in a separate, locked cabinet. The IDIs will be audio-recorded after obtaining informed consent from the participant for the interviews to be recorded. The recordings will be uploaded to a password-protected computer, and Data Associates will transcribe and translate the recording into a Microsoft Word document, which will also be password-protected. Any digital cervical images captured during colposcopy will be stored only in password-protected and de-identified study databases, linked only to the study participant PID. As mentioned above, these images may be shared with sponsors or partners for future research into cervical lesion diagnostics.

All data analysis will be done on datasets which have only the participant ID as a unique identifier. Clinical information with individual identifiers will not be released without the written permission of the participant. We expect these procedures to adequately protect participant confidentiality. However, it is possible that a participant's study participation, HIV or cancer screening status could become known to people in the community and may result in stigma or discrimination. Should that occur, study staff will work with the participant and his/her family as appropriate to resolve the situation in whatever manner is preferred. All study procedures carry minimal risks.

Data collection forms, electronic databases, and printed data will only be supplied to appropriate study staff on an as-needed basis. Any publication about this research study will omit names and any other personally identifiable information. However, individually identifiable private information may be reviewed by the following groups to monitor the conduct of the study and participant safety: The Ministry of Health of Malawi, the Malawi National Health Sciences Research Committee (NHSRC), and the UNC IRB.

